1. PURPOSE OF THE STUDY AND BACKGROUND

1.1. Background

Cardiac resynchronization therapy (CRT) is a demonstrably effective device intervention for patients with broad QRS and ventricular dysfunction and is a class I indication for patients in sinus rhythm, LBBB and EF \leq 30-35%. However, many patients with heart failure (HF) are unable to maintain sinus rhythm and approximately 30-36% of CRT patients are in atrial fibrillation (AF). Unfortunately, there is lack of evidence for the benefits of CRT in the absence of sinus rhythm. The recent RAFT study in patients with less advanced HF found no benefit at all for CRT for permanent AF patients although most patients did not achieve sufficient biventricular pacing.

Approximately 100,000 CRT implants were performed in the US in 2011 at a cost of approximately \$1.8 billion. The absence of CRT benefit in the high-risk subset of AF patients who undergo CRT would generate substantial utilization of health care resources in the form of hospitalization and re-hospitalization, urgent care for HF decompensation, and intensified frequent outpatient management.

There is retrospective and observational data that suggest that only CRT patients with AF who undergo atrioventricular junctional (AVJ) ablation can respond as well as patients in sinus rhythm. AVJ ablation regularizes rhythm, eliminates tachycardia, and forces 100% biventricular pacing without fusion or pseudofusion. In the absence of a randomized clinical trial, however, there are concerns regarding making a significant proportion of CRT patients pacemaker dependent. It is believed that AVJ ablation is performed in only small numbers of patients at the present time.

We propose a randomized controlled clinical trial in 40 subjects with permanent AF who are eligible for cardiac resynchronization therapy with defibrillator (CRT-D) to test the benefit of AVJ ablation on clinical outcome.

1.2. Purpose of the study

The primary aim of the study is:

- To determine if patients with permanent AF who meet conventional criteria for CRT-D and undergo AVJ ablation have improved left ventricular remodeling as assessed by left ventricular end-systolic volume reduction \geq 15% from baseline to 6 months.

The secondary aims of this study are:

- To determine if subjects with permanent AF who meet conventional criteria for CRT-D and undergo AVJ ablation, relative to subjects without AVJ ablation, have:
 1. Improved left ventricular ejection fraction
 2. Diminished left ventricular end-diastolic volume
 3. Lower risk of heart failure requiring augmented oral or IV treatment regimen during an in-hospital stay or IV decongestive therapy outside of a formal inpatient hospital admission
 4. Lower likelihood of experiencing inappropriate implantable cardioverter-defibrillator (ICD) therapy
 5. Lower risk of ventricular tachycardia (VT) or ventricular fibrillation (VF) requiring appropriate ICD therapy
 6. Higher percentage of biventricular pacing
 7. Improved quality of life
 8. Acceptable safety and complication rate in this high-risk heart failure population

2. STUDY DESIGN

2.1. Overview

JAVA-CRT trial is proposed as an unblinded randomized controlled longitudinal trial. At randomization subjects receiving CRT-D implantation for standard clinical indications will be randomized 1:1 to undergo AVJ ablation or to be treated conventionally without AVJ ablation. Subjects will be required to be on optimal medical therapy including maximally tolerated doses of beta-blockers, ACE-inhibitors or ARBs, aldosterone antagonists, and statins, digoxin, and aspirin as recommended by current guidelines. Warfarin or a novel oral anticoagulant will be used for stroke prevention. Beta-blockers and digoxin will be used for rate control of ventricular response. AVJ ablation will be performed at the time of CRT-D implantation. Programming of implantable devices will be by protocol and will intend to provide maximal CRT pacing with attention to rate cutoffs and enhanced features. Subjects will be excluded from the trial if ventricular rates at rest are > 90 bpm despite optimal medical therapy or < 50 bpm, or if they have heart block or symptomatic bradycardia that necessitates permanent pacing.

It will not be possible to perform this trial in feasible and efficient manner as double-blinded. The primary endpoint of left ventricular volume on echocardiogram will be analyzed with the echo core lab blinded to subject treatment assignment. We acknowledge the potential for unblinding if the rhythm recorded on the echocardiogram suggests intact atrioventricular nodal conduction, but this is unavoidable in the pilot study and mitigated by the quantitative analysis of the primary endpoint and efforts at using only recordings with paced beats. The adjudication of secondary heart failure hospitalization endpoints will be done by review of medical records that have had data redacted or removed so that committee members will perform their duties without risk of bias.

2.2. Rationale for Study Design

The main innovation in the trial relates to the concept of the study. As described above, there are no data from a randomized clinical trial establishing evidence for clinical benefit of CRT in AF patients. We realize that this proposal is not designed to assess clinical benefit measured by endpoints of heart failure hospitalization or death, but obtaining proof of concept by demonstrating significant reduction in left ventricular volume will be essential to pursue a more definitive study. Testing the hypothesis that AVJ ablation will result in much more effective CRT pacing is very much needed in light of widespread use of CRT in AF patients without sufficient scientific proof. Knowing that 36% of CRT-D patients present in AF, the economic impact of treatment optimized by adding AVJ ablation will be very significant for health care (assuming the trial proves the hypothesis). Furthermore, since a prior study suggests that even a high percentage of biventricular pacing in the absence of AVJ ablation may not provide for the best possible outcomes from CRT, the proposed study is not only scientifically appropriate but also ethically sound.

3. CHARACTERISTICS OF THE RESEARCH POPULATION

3.1. Subject Characteristics

a) Number of Subjects

This trial will enroll 40 subjects at 20-40 enrolling sites who meet study inclusion and exclusion criteria as described in Section 3.2.

b) Gender and Age of Subjects: Male of female subjects aged 21 years or older. We expect to enroll 25% women.

c) Racial and Ethnic Origin: There are no restrictions on race or ethnicity in this study. We expect to enroll 25% minority subjects.

3.2. Inclusion and Exclusion Criteria

3.2.1. Inclusion Criteria

- Age \geq 21 years on date of consent
- Optimal pharmacologic therapy is defined by published guidelines from the American Heart Association and the American College of Cardiology
- Existing indication for CRT device with initial implant scheduled within 1 calendar month on or from date of randomization
- Ischemic or nonischemic cardiomyopathy
- LVEF \leq 35% within 12 calendar months prior to or on consent date by angiographic, radionuclide, or echocardiographic methods
- NYHA class II-IV (ambulatory) on consent date
- QRS \geq 120 ms for LBBB and \geq 150 ms for non-LBBB patients within 1 calendar year prior to or on consent date
- Continuous AF $>$ 3 calendar months when no further efforts to restore sinus rhythm are feasible or pursued**

***ECG evidence of AF will be required at enrollment and at 2 additional time points, one within 3 calendar months and one \geq 3 calendar months prior to enrollment, with no intervening ECGs revealing sinus rhythm and/or no successful effort to restore sinus rhythm for $>$ 24 hours*

OR

- Active CRT-D device implanted within the last calendar year with $<$ 15% improvement in LVSEV from pre-implant cardiac imaging. The evaluation of LVSEV post implant must be within the last three calendar months.
- Continuous AF $>$ 3 calendar months when no further efforts to restore sinus rhythm are feasible or pursued (see definition above)

3.2.2. Exclusion Criteria

- Ventricular rate $>$ 90 bpm at rest despite maximal medical therapy evidenced on 12-lead ECG within 1 calendar year prior to or on consent date
- Ventricular rate $<$ 50 bpm at rest evidenced on 12-lead ECG within 1 calendar year prior to or on consent date
- Heart block/symptomatic bradycardia that necessitates permanent pacing
- Acute coronary syndrome or coronary artery bypass surgery or percutaneous coronary intervention (balloon and/or stent angioplasty) within 3 calendar months prior to consent date
- Enzyme-positive myocardial infarction within the past 3 calendar months prior to consent
- Severe aortic or mitral valvular heart disease eligible for percutaneous or surgical repair/replacement procedures
- Angiographic evidence of coronary disease that requires coronary revascularization and with likelihood of undergoing a CABG or PCI in the next 3 calendar months following consent date
- Prior AVJ ablation any time in the past
- Any medical condition likely to limit survival to $<$ 1 year
- Presence of ACC/AHA Stage D refractory Class IV symptoms listed for transplant or requiring inotropic support at time of consent.
- Contraindication to systematic anticoagulation
- Renal failure requiring dialysis at time of consent.
- AF due to reversible cause e.g. hyperthyroid state

- Women who are pregnant or plan to become pregnant during the course of the trial** Note: Women of childbearing potential must have a negative pregnancy test within 7 days prior to randomization.
- Participation in other clinical trials that will affect the objectives of this study
- History of non-compliance to medical therapy
- Participation in other clinical trials (observational/lead registries are allowed) with approval from the CDC
- Inability or unwillingness to provide informed consent
- Resides at such a distance from the enrolling site so travel to follow-up visits would be unusually difficult
- Does not anticipate residing in the vicinity of the enrolling site for the duration of the trial
- Short-lived AF or in sinus rhythm

** Women will be allowed to enter this study if surgically sterile, postmenopausal (at least 1 year without periods), or willing to use a medically acceptable method of birth control prior to study entry and while participating in the study.

4. SUBJECT IDENTIFICATION, RECRUITMENT AND CONSENT

4.1. Method Of Subject Identification And Recruitment

Subjects will be recruited from ongoing local referrals of patients indicated for cardiac resynchronization therapy with defibrillator (CRT-D) devices or from patients being medically monitored for an implanted CRT-D device. As indicated above, verification of permanent atrial fibrillation will be required when considering eligible potential subjects.

4.2. Process of Consent

The site investigator and/or study coordinator will consent subjects in this study. The consent document will be used as a guide for the verbal explanation of the study and will be the basis for a meaningful exchange between the investigator and the potential subject. The subject's signature provides documentation of agreement to participate in a study, but is only one part of the consent process. The consent document will not serve as a substitute for discussion and the potential subject will be invited to ask any questions or concerns that will be answered by the study team members. Once a participant indicates that he or she does not want to take part in the research study, this process stops. The potential subject will be given sufficient opportunity to consider whether or not to participate. Refusal to take part or withdraw from the study at any time will not interfere with the future medical treatment.

5. METHODS AND STUDY PROCEDURES

5.1. Study Procedures

This study is designed as a 2-arm unblinded randomized clinical trial. A total of 40 subjects receiving or with CRT-D devices for standard clinical indications will be randomized 1:1 to the atrioventricular junctional (AVJ) ablation or to a control arm without ablation, stratified by enrolling site. All subjects will be followed for 6 months. The study procedures to be conducted for each subject enrolled in the study are presented in tabular form (Schedule of Activities) below and described in the text that follows:

Table 1. Schedule of Activities

PROCEDURES	Screening Visit	Randomization - Baseline – Procedure Visits		Follow-up Visits		
	Visit 1	Visit 2	Visit 3	Visit 4	Visit 5	Visit 6
	Consent within 1 calendar month prior to randomization	Day 1	Within 1 calendar month after randomization date	1 calendar month \pm 7 days	3 calendar months \pm 14 days	6 calendar months \pm 14 days
	Screening	Randomization-Baseline	Ablation \pm CRT-D	1 month post randomization	3 months post randomization	6 months post randomization
Informed Consent	✓					
Pregnancy test when applicable (within 7 days prior to randomization date)	✓					
Eligibility Confirmation	✓					
Randomization		✓				
Demographics /Medical History		✓				
Physical Exam (Limited)		✓		✓	✓	✓
CV Medication Prescribed		✓			✓	✓
Symptom Assessment		✓		✓	✓	✓
Quality of Life		✓**				✓
12-lead ECG		✓*		✓*	✓*	✓*
Echocardiogram		✓*				✓
CRT-D Implantation†			✓*			
CRT-D Programming /Episode Reports			✓*	✓*	✓*	✓*
AVJ ablation			✓*			
Adverse Event			✓	✓	✓	✓
Heart Failure Event				✓	✓	✓
Protocol Deviations		✓	✓	✓	✓	✓
Subject Status			✓	✓	✓	✓

* standard of care procedures

** obtain quality of life questionnaire prior to informing subject of treatment assignment

† Ablation only for active CRT-D devices

CRT-D Implantation and Programming: For subjects having an index device procedure, the CRT-D will be implanted following clinically approved indications using standard techniques and leads will be placed in the right ventricle (RV) and the coronary sinus for biventricular (BiV) pacing. In case left ventricular (LV) lead cannot be positioned in the coronary sinus, direct epicardial techniques are permitted

For primary prevention subjects (indicated for ICD without prior cardiac arrest or hemodynamically compromising VT/VF), ICD programming should follow parameters shown in Table 2 below. These programming recommendations have been shown to reduce the risk of inappropriate and appropriate ICD therapies and increase survival. For secondary prevention subjects (indicated for ICD due to prior cardiac arrest or hemodynamically compromising VT/VF), the ventricular tachycardia zone should be programmed at a rate commensurate with the subject's documented clinical arrhythmia; however, the ventricular fibrillation zone should remain at 200 bpm or greater (Table 3).

Table 2. CRT-D Programming Recommendations - Primary Prevention	
Rate in Single VT Zone	At least 185-200 bpm
Delay	At least 6-12 secs or 30 intervals
ATP Therapy	On for all zones (at least 1 attempt, 8 stimuli, 84-88% of TCL, burst)
Shock Energy	Maximum for all shocks
Discrimination Algorithms	On for rhythms > 200-230 bpm
Discriminator Time-out	Off
Lead Failure Alerts	On
Noise Detection and T-wave Oversensing	On
VT Monitoring Zone	On

Table 3. CRT-D Programming Recommendations - Secondary Prevention	
Rates for Single/Dual Zones	(1) 10-20 bpm below clinical VT rate, if known; (2) For 2 nd zone if desired, at least 185-200 bpm
Delay	At least 6-12 secs or 30 intervals
ATP Therapy	On for all zones (at least 1 attempt, 8 stimuli, 84-88% of TCL, burst)
Shock Energy	Maximum for all shocks
Discrimination Algorithms	On
Discriminator Time-out	Off
Lead Failure Alerts	On
Noise Detection and T-wave Oversensing	On
Additional VT Monitoring Zone	Optional

All subjects should maintain rate-responsive BiV VVIR pacing throughout the study. In all patients, the pacemaker should be programmed to a VVIR mode with a lower rate of 80 bpm for the first calendar month after implant to mitigate the risk of polymorphic ventricular tachycardia for those patients undergoing AV junction ablation. Following that the rate can be decreased to 60 ppm during routine clinical care. The pacemaker should be programmed in a VVIR mode with a lower rate of 60 bpm and an upper sensor rate set at 80% of age-corrected maximum heart rate. The upper sensor rate should remain unchanged throughout the study. Device algorithms designed to promote fusion and increased pacing during atrial fibrillation (e.g. ventricular sensed response, trigger pacing, ventricular rate regularization) should remain programmed ON throughout the study. Patients randomized to either arm of the study are programmed in a similar fashion, as they are both in permanent AF. Should sinus rhythm spontaneously develop, or as a result of shock in response to VT, the device may need to be reprogrammed to a dual chamber mode.

AV Junction Ablation Procedure: At the discretion of the investigator, ablation of the AVJ should be performed within 2 days of implantation of a market-released CRT defibrillator (CRT-D) device (unless active CRT-D device has been implanted), although specific institutional or subject circumstances may necessitate a delay of up to 7 days. For subjects with a previously implanted CRT-D device, ablation must take place within 30 days of randomization. Ablation of the AV junction is a relatively simple procedure. Ablation is usually targeted at the atrial side of the tricuspid valve annulus in the region of the compact AV node. A deflectable ablation catheter is placed on the annulus where it records a large His-bundle electrogram. The catheter is then withdrawn until it records a large atrial electrogram and small His-bundle electrogram. It is at this site that radiofrequency at 30-50W is delivered for up to 60 secs; if complete heart block does not ensue, the ablation catheter is repositioned and the process repeated. A prior study has demonstrated that the procedure can be successfully performed in >99% of patients. For rare subjects for whom there is difficulty, ablation can also be performed successfully at the left intraventricular septum using a retro-aortic approach. If conduction recovers, which is rare, the ablation will be repeated. There conceivably may be a very rare subject who fails both approaches, and these subjects will be followed in their assigned arm and treated with medical therapy for rate control, i.e. intent to treat. The cardiac rhythm will be observed for at least 30 minutes following ablation to ensure the persistence of complete heart block with either ventricular asystole or a stable and regular escape rhythm. Additional AVJ ablation procedures may be performed if the first procedure is not successful. AVJ ablation is routinely performed in clinical practice and is routinely reimbursed. However, despite these practices there is no evidence from randomized clinical trials regarding clinical benefit of this procedure in those undergoing CRT-D implantation.

Randomization as a method of experimental control has been extensively used in human clinical trials. It prevents the selection bias and insures against accidental bias. It produces the comparable groups and eliminates the source of imbalance after treatment assignment. Finally, it permits the use of probability theory to express the likelihood of chance as a source for the difference of the final outcome. Randomization in this study will occur at visit 2. It should be noted that that visit 2 could take place on the same day as visit 1 and visit 3.

1. CRT-D device implantation or
2. CRT-D device implantation and AVJ ablation procedure

For subjects with an existing CRT-D device

1. Ablation
2. Medical management

Subjects will be notified that randomization is part of this study during the consent process. Subject will be informed which randomized arm they have received after completing the quality of life questionnaire. Subject will be notified that either treatment arm may be less or more effective, or may have more or less side effects.

Randomization will be stratified by enrolling site and generated per the scheme described in Section 11. The randomization strings for treatment assignment will be provided to the database programmer at the coordination site by chief statistician [name] and uploaded in the electronic data capture system with appropriate testing and validation that the system is working correctly prior to the beginning of subject

randomization. The enrolling site has full responsibility for completion of the CRFs required for subject randomization. The enrolling site may contact the data center project manager and will notify about randomization results only if the enrolling site has no internet access or the web base program will automatically assign the randomization treatment assignment and subject ID based on the randomization strings provided by the biostatistician. The randomization result is viewed by the enrolling site in the eDC system following randomization or documented on the paper CRF which is returned to the enrolling site if randomization cannot be done through the eDC system. All eligibility criteria will be confirmed prior to providing the randomization treatment assignment/subject ID to the enrolling site.

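### The 80 bpm period meant to prevent polymorphic VT after AVJ ablation is timed from implant, so for subjects with an existing CRT-D it has usually ended by ablation

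*Combined protocol and SAP*

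**What the plan says.** - **Pacing rate (Section 5.1, CRT-D Implantation and Programming).** All devices get a "lower rate of 80 bpm for the first calendar month after implant to mitigate the risk of polymorphic ventricular tachycardia". The sentence names patients having AVJ ablation as those to be protected. The rate may then come down in routine care, and the standing instruction follows: "The pacemaker should be programmed in a VVIR mode with a lower rate of 60 bpm". The same paragraph adds: "Patients randomized to either arm of the study are programmed in a similar fashion".
- **Second entry route (Section 3.2.1).** Subjects may enter with "Active CRT-D device implanted within the last calendar year with" less than 15% improvement in LV end-systolic volume. The post-implant evaluation must fall within the last three months. No minimum time since implant is given.
- **Schedule (Section 5.1, Table 1).** The footnote on the implantation row reads "Ablation only for active CRT-D devices", so these subjects have no new implant date. The row "CRT-D Programming /Episode Reports" is ticked at Visit 3, the procedure visit, without parameters.
- **Ablation timing (Section 5.1, AV Junction Ablation Procedure).** For new implants, ablation is due within 2 days of implant, or up to 7 if circumstances require. "For subjects with a previously implanted CRT-D device, ablation must take place within 30 days of randomization." On later loss of block: "If conduction recovers, which is rare, the ablation will be repeated."
- **Procedure visit (Section 5.5).** Device programming is to be adjusted when the AVJ is ablated, by reference to the earlier text.
- **Risks (Section 8.1).** Polymorphic VT is one of two feared late complications. The section says it can be eliminated by starting at a higher lower rate and stepping down, and that the trial has been designed this way.

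**The concern.** The purpose of the 80 bpm rule is tied to ablation, but its clock is tied to implant. In new implants the two dates nearly coincide and the rule works. In the existing-device cohort they can be many months apart. A site that follows the programming paragraph to the letter can ablate such a subject, leave the lower rate at 60 bpm, and commit no deviation. A site that reads Section 5.5 by its evident intent will program 80 bpm. The protocol thus supports two settings for the same newly ablated, possibly pacemaker-dependent subject, and the literal one omits the preventive step on which the risk section relies. A repeat ablation more than a month after implant has the same gap, though the protocol calls recovery of conduction rare.

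The stake is subject safety in one of the two entry cohorts. The primary endpoint and the power calculation are not in question.

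**Working it through.** The plan gives no figure to reproduce. The check sets the dates side by side and then asks whether 'usually' is justified.

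**1. Time at 80 bpm after ablation, as written**

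- New implant: ablation 0 to 7 days after implant and a calendar month of 28 to 31 days leave 28 − 7 = 21 to 31 − 0 = 31 days.
- Existing device, implanted more than a month before ablation: 0 days.

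**2. How often the month has ended by ablation**

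The documents give only the outer limits: implant up to one year before entry, consent within one month before randomization, ablation within 30 days after randomization. The distributions below are assumptions.

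Let T be days from implant to consent, uniform over a span S, and D days from consent to ablation. Taking the month as 30 days:

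share past the month = 1 − E[max(0, 30 − D)] / S

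| Delay D | E[max(0, 30 − D)] | S = 365 | S = 182 |
|---|---|---|---|
| 0 (all on one day) | 30 | 1 − 30/365 = 91.8% | 1 − 30/182 = 83.5% |
| uniform 0–30 | 15 | 1 − 15/365 = 95.9% | 1 − 15/182 = 91.8% |
| uniform 0–31 plus uniform 0–30 | 30³/(6 × 31 × 30) = 4.84 | 98.7% | 97.3% |

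A deliberately unfavourable case puts most implants shortly before entry: T exponential with mean 3 months, truncated at 12. With no delay the share is (e^(−1/3) − e^(−4)) / (1 − e^(−4)) = (0.7165 − 0.0183) / 0.9817 = 71%. With delay uniform over 0–30 days it is 85% (by simulation). If every subject is at least one month past implant, it is 100%.

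The range is therefore 71% to 100%, a majority in every case. It largely restates that a one-year window is much longer than a month. The required post-implant imaging also makes very recent implants less likely.

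**3. Mean time left at 80 bpm, existing devices, S = 365**

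- Same-day ablation: 30² / (2 × 365) = 1.2 days.
- Delay uniform 0–30: E[(30 − D)²] / (2 × 365) = 300 / 730 = 0.4 days.

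**4. Does any other text restart the clock?**

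- Table 1 schedules programming at Visit 3 but gives no rate.
- Section 5.5 gives a trigger, the time of ablation. The only lower-rate text it can refer to is the Section 5.1 paragraph, which supplies 80 bpm and one month but counts from implant.
- Section 8.1 shows the intent and sets no rule.

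None of them starts a new month at ablation.

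**5. With the month counted from ablation**

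Every ablated subject gets 28 to 31 days at 80 bpm after ablation, whichever way they entered.

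**The case against.** The best reply is that the protocol already points to the right answer. Section 5.5 expressly covers subjects with an existing device, ties reprogramming to ablation, and leads back to the only rate given for ablated patients. For a new implant already at 80 bpm that instruction would change nothing about the lower rate; for a device at 60 bpm, raising it is the natural meaning. The 60 bpm sentence follows the 80 bpm period and reads as a maintenance setting. Section 8.1 confirms the intent. Every subject has a defibrillator, and the DSMB's main focus is events attributable to ablation (Section 9).

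Much of this stands. A reader might infer that sites have no programming instruction at ablation, or that all existing-device subjects will be left at 60 bpm. The documents support neither: there is a trigger and a cross-reference, and a careful site would reach 80 bpm.

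What does not stand is that the gap is closed. The cross-reference returns the reader to a clock that has normally run out, and 60 bpm remains a compliant reading. The defibrillator treats the arrhythmia and does not prevent it; the protocol requires 80 bpm although every subject has one. DSMB review comes after the event.

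**Conclusion.** The concern holds and should be fixed. As written, the rule gives the wrong setting for one entry cohort: the 80 bpm month has usually ended by ablation, and no text restarts it. 'Usually' rests on assumed implant-to-entry times, since no minimum is stated, but it held in every scenario tried.

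Three further inferences are tempting and unsupported.

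- **A count of affected subjects.** The existing-device share of the 40 subjects is not stated, and randomization is stratified by site, not by device status (Section 11).
- **An excess risk.** The roughly 5% sudden death in Section 8.1 comes from early ablation trials, and the 2 of 252 (0.8%) arrhythmic deaths from pacemaker patients managed with a higher initial rate. Neither measures the risk at 60 bpm in subjects with a defibrillator.
- **An effect on the primary endpoint or power.** Nothing in the documents shows one.

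**What to change.** - In the Section 5.1 programming paragraph, let the 80 bpm month run from implant or from AVJ ablation (including a repeat ablation), whichever is later.
- In Section 5.5, replace the general back-reference with an explicit reference to this rule.
- Beside the statement that the arms are programmed alike, record the month after ablation as an exception.

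The change itself is one sentence, two consequential edits and a note to sites. Some subjects will step down later or need one extra device check. For example, for an ablation on day 30 after randomization the new month ends around day 60, after Visit 4 (day 23 to 37 on a 30-day month). If the step-down then waited for Visit 5 (3 months taken as 91 days, ± 14), the time at 80 bpm would be (91 − 14) − 30 = 47 to (91 + 14) − 30 = 75 days. A separate check avoids this.

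The existing-device arms would differ in lower rate for about one month of six (1/6 = 17% of follow-up). In ablated subjects little effect on percentage biventricular pacing is expected, because Section 1.1 says ablation already forces it to 100%. The other effects of the difference cannot be sized from the documents.
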